Official title:

Blocking nocturnal blue light to treat insomnia: A pilot randomized controlled trial

NCT #:

NCT0268800

Date of Document:

July 26, 2018

Study Design:

The current proposal is for a randomized, placebo-controlled, crossover trial to test the effects of blocking nocturnal blue light exposure on sleep, sleep habits, and melatonin secretion in individuals with insomnia. This will be a combined ambulatory and laboratory investigation. The intervention will consist of wearing BB lenses which block 97% of blue light (Uvex amber lenses, Bandit wraparound glasses, Honeywell Safety, Smithfield, RI) or non-BB placebo lenses (Uvex clear lenses, Bandit wraparound glasses, Honeywell Safety, Smithfield, RI) for the 2 h preceding bedtime each night for 1 wk (**Fig. 2**). Intervention phases will be separated by a 4-wk washout period, to reduce carry-over effects and study premenopausal women at the same menstrual cycle phase. This will be followed by crossover to the alternate intervention phase. Each 1-wk intervention phase will conclude with an in-

[figure not shown]

Figure 2. The randomized, placebo-controlled, crossover design. AW: actiwatch; SSQ: subjective sleep quality.

patient laboratory visit to characterize the effects of the intervention on sleep and circadian physiology (**Fig. 3**). During the ambulatory portion, participants will be free-living and will expose themselves to their habitual light levels and choose their sleep timing. During the laboratory portion, an 8-h sleep episode will be scheduled based on participant's habitual sleep times during the week preceding entry. For standardization, and to demonstrate the beneficial effects of the BB lenses for preserving nocturnal melatonin secretion, participants will be uniformly exposed to an LED light source for 2 h preceding bedtime during the laboratory portion (**Fig. 3**).

Potential participants who reply to posted advertisements will be told about the study. They will then be scheduled to meet with research staff to sign consent forms and determine eligibility. Inclusion criteria will include age 18-65 y, and a report of insomnia for ≥ 1 month. To determine insomnia, participants will have scores indicative of the case definition of insomnia based on the Insomnia Symptoms Questionnaire. This validated questionnaire assesses the presence, frequency, and duration of symptoms, as well as daytime consequences. Symptoms assessed include difficulty initiating sleep, difficulty maintaining sleep, and experiencing sleep that is unrefreshing. Participants with a diagnosis of obstructive sleep apnea of at least moderate severity (apnea-hypopnea index ≥ 15 events/h), a STOP-BANG score > 5 indicative of a high risk of sleep apnea, or other sleep disorders such as periodic limb movement disorder or narcolepsy will be excluded. History of deep vein thrombosis will be exclusionary. Night or rotating shift workers, those who have traveled across time zones in the 2 wk preceding procedures, will be excluded, since these can affect circadian physiology. Participants will be free of any psychiatric or neurological disorders, as these can affect sleep/circadian rhythms. Participants will be excluded if they are smokers or taking beta-blockers (26), since these decrease melatonin release, or if they consume excessive caffeine (>500 mg/d). Hypnotics/sedatives for sleep can have been used, but participants will refrain from use for 2 wk preceding the start and throughout

the study. Participants with children <1 y-old will not be included. Women will not be pregnant or breastfeeding. CUMC research staff will be involved in the recruitment and enrollment efforts.

Individuals meeting inclusion criteria will be enrolled and randomized to receive either BB or placebo lenses in phase 1. Participants will be instructed to wear lenses each night, from 2 h before bedtime until lights out. Throughout the intervention, upon awakening participants will note their bedtime and waketime, and time of wearing lenses, on a sleep-log, and will complete a daily post-sleep questionnaire (**PSQ**). The PSQ entails quantitative estimates of SOL, total sleep time (**TST**), time awake during sleep episode, and number of awakenings, as well as ratings on a 7-point scale of overall evaluation of sleep (1: extremely bad, 7: extremely good), soundness of sleep (1: extremely light, 7: extremely sound), current feeling of sleepiness (1: not sleepy at all, 7: extremely sleepy), and current feeling of refreshed (1: not refreshed at all, 7: extremely refreshed) (42). This will allow us to confirm compliance with intervention and to collect data on ambulatory sleep quality and habits across the trial. During each intervention, participants will wear a wrist-mounted Actigraph GT3X+ to monitor TST, SOL, and sleep efficiency (**SE**). At the beginning of the intervention, participants will complete a brief computer-based adaptive neuropsychological battery (NIH Toolbox Cognition Battery; www.nihtoolbox.org) to assess their functioning in the domains of executive function, attention, episodic memory, language, processing speed, and working memory. This assessment will last about 30 minutes. CUMC research staff will interact with participants and setup the study.

Upon completing the 1-wk intervention, participants will be admitted to the Inpatient Unit at the Clinical Research Resource (CRR) of CUMC at ~18:00 for the lab testing period (Fig. 3). Upon admission, an in-dwelling forearm catheter will be inserted to allow continuous blood sampling which will not interrupt the sleep episode. Blood (3 ml/sample) will be collected continuously (1x/h) from 19:00-09:00 under “constant posture conditions”. Participants will remain in dim lights (<30 lux) and in a semi-recumbent position during wakefulness. The sleep episode will occur in total darkness in a fully recumbent position. In lieu of meals, small isocaloric servings of BOOST Plus Complete Nutritional Drink (Nestle) will be served each hour during wake episodes. Participants will be asked to stretch their legs each hour while in the bed during the lab portion, without getting out of bed.

Within the first 2 hours of arrival in the lab, participants will complete the Pittsburgh Insomnia Rating Scale-65 (**PIRS65**), which quantifies insomnia symptom severity. They will also repeat the same brief (~30 min) neuropsychological battery (NIH Toolbox Cognition Battery) administered at the intervention. Each hour spent awake in the laboratory, participants will complete a 15-item visual analogue scale (**VAS**) to assess their levels of alertness, hunger, and appetite. CUMC research staff will interact with participants and conduct the study/collect data.

Beginning 2 hours before the sleep episode, participants will be exposed to bright light (500 lux) and will wear either BB or placebo lenses. The sleep episode will be scheduled based on their habitual sleep patterns during the previous week at home. They will have an 8-hour sleep opportunity in the lab. This will include a polysomnographic sleep recording. Upon awakening, participants will remain in bed in semi-recumbent position for the next 3 hours. Participants will complete the PSQ, and will resume the VAS scales, as well as have servings of BOOST Plus. At

9:00, blood sampling will end and the catheter will be removed. Participants will be discharged at 10:00. Blood samples will be analyzed for plasma content of melatonin (RIA, ALPCO, Salem, NH). After discharge, participants will begin a 4-week washout period. At the conclusion of this, they will cross over to the alternate lenses condition. They will be given the alternate lense type (BB or clear) and also the actigraph for the 7-day ambulatory tracking period. They will resume using the lenses 2-h before bedtime for 7 days, and completing the sleep-log and post-sleep questionnaires. After this, they will return to the lab for the second overnight visit. At the conclusion of the second overnight visit, they will have completed all experimental procedures.

Statistical Procedures:

Two-way within subjects ANOVA for repeated measures (factors: condition x time) will be used to analyze continuous melatonin, VAS, and neuropsychological values obtained during the laboratory visits. Simple main effects tests will be used to analyze significant interactions. Paired-samples t-tests will be used to analyze single-value sleep parameters (subjective, actigraphic, and PSG), as well as sleep related questionnaires (PIRS65 and PSQ). Data will be tested for normality, and non-parametric equivalent tests will be used if data are deemed not normally distributed. Significance will be $p < 0.05$

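### The 4-week washout does not put premenopausal women at the same menstrual phase: corresponding visits fall 35–36 days apart, 7–8 days out of phase for a 28-day cycle

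*Combined protocol and SAP*

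**What the plan says.** The opening paragraph of Study Design sets the washout and its purposes: "Intervention phases will be separated by a 4-wk washout period, to reduce carry-over effects and study premenopausal women at the same menstrual cycle phase."

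The rest of the section fixes the calendar:

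- The first lab visit comes after the first lens week: "Upon completing the 1-wk intervention, participants will be admitted to the Inpatient Unit at the Clinical Research Resource (CRR) of CUMC at ~18:00." Discharge is at 10:00 the next morning.
- The washout starts there: "After discharge, participants will begin a 4-week washout period."
- It ends when the second lens week begins: "At the conclusion of this, they will cross over to the alternate lenses condition."
- A full second lens week follows: "They will resume using the lenses 2-h before bedtime for 7 days."
- Only then comes the second lab night: "After this, they will return to the lab for the second overnight visit."

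The text has no cycle tracking, cycle-day booking, visit window or assumed cycle length. Eligibility covers ages 18–65 and sets no menstrual criterion, so premenopausal women can enrol.

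**The concern.** Measuring a woman twice at the same point of her cycle requires the interval between the two measurements to be a whole number of her cycles. A four-week figure suggests a 28-day cycle. Here, however, the four weeks are the gap between the end of one phase and the start of the next. The interval that matters, from first lens night to first lens night or from lab night to lab night, is longer by the length of one phase.

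The outcomes in Statistical Procedures are compared within person, by repeated-measures ANOVA and paired t-tests. Any cycle effect on melatonin or sleep that differs between the two visits goes into the error of those comparisons. Controlling it is the stated aim of the spacing. If the spacing does not do so, premenopausal women contribute noise that the plan says has been designed out, and a reader would credit the trial with a control it lacks.

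**Working it through.** **Inputs from Study Design.** Lens week: 7 days. Lab stay: one night, discharge the next morning. Washout: 28 days from discharge to lens restart. Second phase: same structure as the first.

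**Inputs assumed, because the documents do not give them.** Cycle length C (26 to 32 days shown), regular cycles, a starting day spread evenly over the cycle, a 14-day luteal phase for the split into halves, and a sinusoidal cycle effect for the variance comparison.

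**Step 1: the calendar.** Day 1 is the first lens night. The text leaves open whether the lab night is the seventh lens night or follows seven nights at home, so both are shown.

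| | Lab night is night 7 | Lab night follows 7 home nights |
|---|---|---|
| Lab visit 1 | day 7 | day 8 |
| Discharge | day 8 | day 9 |
| Lens restart (discharge + 28) | day 36 | day 37 |
| Lab visit 2 | day 42 | day 44 |
| Start to start | 36 − 1 = 35 days | 37 − 1 = 36 days |
| Lab to lab | 42 − 7 = 35 days | 44 − 8 = 36 days |

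Start-to-start and lab-to-lab intervals agree, so the home week and the lab night are displaced equally.

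**Step 2: the phase offset.** The offset d is the remainder of 35 or 36 after division by C. For C = 28, d = 7 or 8.

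**Step 3: how often the two lab nights fall in opposite halves of the cycle.** With an evenly spread starting day the share is 2d/C. For C = 28 this is 14/28 = 0.500 or 16/28 = 0.571. With visits booked without regard to cycle it is 2 × 14 × (C − 14)/C²; for C = 28, 2 × 14 × 14/28² = 0.500. Matched visits would give 0.

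**Step 4: cycle-related variance of the paired difference.** For a sinusoidal effect of amplitude A, the mean difference is 0 and the variance is A²(1 − cos(2πd/C)). For C = 28 this is 1.000 A² at d = 7 and 1.223 A² at d = 8. Two unrelated cycle phases give 1.000 A²; matched visits give 0.

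| Cycle length | Offset (days) | Opposite halves | Variance relative to unplanned timing |
|---|---|---|---|
| 26 | 9–10 | 69–77% | 1.57–1.75 |
| 28 | 7–8 | 50–57% | 1.00–1.22 |
| 30 | 5–6 | 33–40% | 0.50–0.69 |
| 32 | 3–4 | 19–25% | 0.17–0.29 |
| Unplanned timing | – | 49–50% | 1.00 |
| Matched | 0 | 0% | 0 |

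Only cycles of about 35–36 days bring the offset to roughly zero.

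**Step 5: the washout that would match.** One cycle between lab visits requires a washout of C − 7 or C − 8 days: 18–19 at 26 days, 20–21 at 28, 22–23 at 30 and 24–25 at 32. Two cycles require 2C − 7 or 2C − 8; at 28 days, 56 − 7 = 49 or 56 − 8 = 48.

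**The case against.** The case for leaving the plan alone has four parts.

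- **No printed figure is wrong.** The documents give neither a cycle length nor a lab-to-lab interval; the 28 days is inferred, and four weeks may be a round number with same-phase testing guiding the actual booking. It is true that 28 days is an assumption. But the fixed gap is the only mechanism the plan offers, and rounding does not turn a gap from discharge to restart into a 28-day interval between visits.
- **Figure 2, the design schematic, could not be seen.** This limit is real. Still, the opening paragraph and the closing description of the washout agree that the four weeks lie between the phases, and a drawing would not override both.
- **The schedule does help some women.** This stands. At 30 days about 31–50% of the cycle-related variance is removed relative to unplanned timing, and at 32 days about 71–83%. The statement that nothing is gained applies to 28 days; at 26 days the schedule is worse than unplanned timing. The variance ratios and half-cycle shares also rest on stacked assumptions, whereas the 35–36 day interval and the offsets need only the calendar and a cycle length.
- **The consequences are small.** Order is randomized, the average shift in a cyclic outcome is zero, and the paired error already contains the noise. In a pilot, a sponsor could reasonably accept it and keep one uniform gap. That is a fair choice, but it argues for dropping the phase-matching claim, not for keeping it.

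**Conclusion.** The concern holds. As written, the plan assigns the washout a property that its own schedule does not have. The 35–36 day interval follows from the text alone. The 7–8 day offset adds only the assumption of a 28-day cycle, and no cycle length from 26 to 32 days brings the visits into phase.

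The harm is limited to precision and to the accuracy of the design claim. The lens comparison is not biased and its tests remain valid. Men and postmenopausal women are unaffected, and the washout still serves its carry-over purpose. The documents give neither the share of premenopausal women nor the size of any cycle effect on melatonin or sleep, so the loss of precision cannot be put in outcome units. It should be fixed because the statement is wrong and correcting it is cheap, not because the main comparison is threatened.

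**What to change.** Choose one of two changes to Study Design.

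**(a) Deliver the matching.** For premenopausal women, book the second phase so that the interval from lab visit 1 to lab visit 2 equals one of the woman's own cycles, using the washouts in step 5. If at least four weeks of washout must be kept, use two cycles. The cost is a washout that differs between participants. For a 28-day cycle it is either about one week shorter than stated (20–21 days), which gives up some carry-over protection, or about three weeks longer (48–49 days), which lengthens participation.

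**(b) Drop the claim.** Keep the uniform four-week gap and delete the menstrual-phase purpose from the opening paragraph, leaving carry-over as the only reason given. This costs one clause and leaves the cycle-related noise where it is.

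Statistical Procedures needs no change under either option. Recording the first day of the last menses at each lab visit would allow a sensitivity analysis by cycle phase; it is optional.

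### The 3-hour post-wake period and the 10:00 discharge conflict for bedtimes after 23:00, and the complete-cell ANOVA does not fit VAS ratings taken only while awake (minor)

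*Combined protocol and SAP*

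**What the plan says.** All of this is in the combined protocol and SAP, under Study Design (laboratory procedures) and Statistical Procedures.

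- **Sleep timing.** "The sleep episode will be scheduled based on their habitual sleep patterns during the previous week at home". On its length: "They will have an 8-hour sleep opportunity in the lab". The week in question is the lens week before that visit, when participants choose their own sleep times.
- **Light and lenses.** "Beginning 2 hours before the sleep episode, participants will be exposed to bright light (500 lux) and will wear either BB or placebo lenses".
- **Morning.** "Upon awakening, participants will remain in bed in semi-recumbent position for the next 3 hours". The clock times that follow are fixed: "9:00, blood sampling will end and the catheter will be removed. Participants will be discharged at 10:00".
- **Blood.** "Blood (3 ml/sample) will be collected continuously (1x/h) from 19:00-09:00".
- **VAS.** "Each hour spent awake in the laboratory, participants will complete a 15-item visual analogue scale". Admission is at about 18:00.
- **Analysis.** "Two-way within subjects ANOVA for repeated measures (factors: condition x time) will be used to analyze continuous melatonin, VAS, and neuropsychological values". The text does not say whether time means clock hour or hours from lights-out.

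The eligibility text excludes night and rotating shift workers but puts no limit on habitual bedtime. Fig. 3, cited for the laboratory visit, is not shown in the copy reviewed.

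**The concern.** Some laboratory events are tied to the participant's own bedtime (light, lenses, sleep, waking) and others to the clock (blood sampling, discharge). Two things follow.

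First, the morning schedule may be impossible to follow for later sleepers, which leaves staff to choose which instruction to drop.

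Second, a classical two-way within-subject ANOVA needs every participant to have every time cell under both conditions. VAS starts from admission for everyone, but it stops at bedtime and restarts at waking, so participants with different bedtimes fill different cells. Statistical Procedures gives no rule for incomplete cells. Software that deletes incomplete cases could discard many participants, or all of them.

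For melatonin the question is whether one clock-hour cell means the same thing in every participant. The 2-hour light exposure before bed is where the plan expects to show that the lenses preserve melatonin, so blurring that window bears on a stated aim.

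**Working it through.** The documents give no bedtime distribution and no between-visit shift. The bedtimes below are assumptions.

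**(a) Timeline.** Let B be bedtime and L the time from bedtime to waking. The post-wake period ends at B + L + 3 h.

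- Discharge at 10:00 requires B + L + 3 h ≤ 10:00. With L = 8 h, B ≤ 23:00.
- Overrun with L = 8 h: 0.5 h at 23:30, 1 h at 00:00, 2 h at 01:00.
- Earlier waking moves the limit: L = 7 h gives 00:00, and L = 6 h gives 01:00.
- The end of sampling is a separate limit. Waking by 09:00 requires B + 8 h ≤ 09:00, so B ≤ 01:00. For later bedtimes sampling stops before scheduled waking.

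**(b) VAS cells.** From 18:00 to 10:00 is 16 h. Less 8 h of sleep, each participant has 8 awake hours:

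| Bedtime | Evening hours | Morning hours |
|---|---|---|
| 22:00 | 4 | 4 |
| 23:00 | 5 | 3 |
| 00:00 | 6 | 2 |

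Across the three bedtimes, evening has 6 cells observed and 4 common to all, and morning has 4 observed and 2 common. In total 6 + 4 = 10 are observed and 4 + 2 = 6 are common. Each participant has 8 of the 10, so listwise deletion over all observed cells leaves nobody. The count is the same on clock hour and on hours from lights-out. For bedtimes 22:00–23:00 it is 9 observed and 7 common; for 22:00–01:00, 11 and 5.

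These counts assume that the 10:00 discharge governs. If later sleepers instead complete the 3 h and others stay to 10:00, the 00:00 sleeper gains one morning hour. For 22:00–00:00 the counts become 11 observed and 6 common on clock hour, and 10 and 7 on lights-out time.

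**(c) Melatonin.** Hourly samples from 19:00 to 09:00, counted as points, give 15 cells, and every participant has all 15. The states are dim light before B − 2 h, 500 lux from B − 2 h to B, sleep from B to B + 8 h, then post-wake.

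- *Mixing across participants.* With bedtimes of 22:00 and 23:00, three cells differ: 20:00 (light or dim), 22:00 (sleep or light) and 06:00 (awake or asleep). That is 3 of 15. For 22:00–00:00 it is 6 of 15, and for 22:00–01:00 it is 8 of 15.
- *Shift between visits.* The same three changeovers move if one participant's bedtime differs by 1 h between visits, so 3 of 15 cells compare different states between conditions.
- *Interaction signal.* Suppose a constant lens effect confined to the 2-h light window, bedtimes split equally on whole hours, and the same bedtime at both visits. Let d be the share of participants with the effect present in a cell, and take the sum of (d − mean d)². For 22:00–23:00 on clock hour, d is 0.5, 1 and 0.5 in three cells and 0 elsewhere: 1.5 − 4/15 = 1.233. On lights-out time with 14 common cells: 2 − 4/14 = 1.714. The ratio is 72%. For 22:00–00:00 it is 0.844/1.692 = 50%. If the effect lasts 4 h from light onset, the ratios are 85% and 74%. With one common bedtime nothing is lost.
- *Mean condition effect.* Each participant has 2 affected cells of 15 whatever the bedtime, so the mean on clock hour is 2/15 of the effect in every scenario. Bedtime spread costs it nothing.

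**The case against.** The strongest reply is that the plan may be simpler than this makes it look. Bedtime at 23:00 plus 8 h plus 3 h is exactly 10:00, so the times fit one nominal schedule, and Fig. 3 may show that schedule and define the time axis. This stands as a caution: the plan cannot be said to lack a time axis, only that its text does not give one. It does not remove the conflict, because the text individualises bedtime and sets no limit.

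A second reply is that blood is drawn at fixed clock hours, so time as scheduled sample is complete and balanced. That also stands. A reader might infer that the melatonin comparison is biased, but with the same bedtime at both visits each clock-hour cell compares a participant in the same state under both lenses. Bias from mixed states needs a between-visit shift. That is possible, since each bedtime comes from its own lens week, but the documents give no figure for it. Nor are the 72% and 50% ratios power losses: they concern the interaction only and leave out error variance and degrees of freedom.

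A reader might also infer that lights-out should be the primary melatonin axis. The documents do not settle this. Melatonin is circadian, and after a 1-h shift the lights-out axis matches states in all 14 common cells but compares each of them 1 h apart on the clock. It is a trade-off.

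Finally, VAS does not follow bedtime throughout; only its stop and restart do. That is enough to leave cells empty. The neuropsychological battery is given at the start of the intervention and on arrival, so bedtime does not affect its time factor.

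**Conclusion.** The point holds, at minor severity, in three parts.

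- **Schedule.** The two morning rules are incompatible for bedtimes after 23:00 if waking is at 8 h. How many participants this affects is unknown. It does not alter the melatonin data, because sampling ends at 09:00 under either rule.
- **VAS.** This is the firmest analytic part. When bedtimes differ by an hour or more, cells are missing by design on either time axis, and the stated ANOVA has no rule for them. The size (10 observed, 6 common) rests on assumed bedtimes of 22:00–00:00 and on discharge at 10:00.
- **Melatonin.** The planned analysis is workable. Clock hour may dilute the interaction, and a between-visit shift would make some cells compare unlike states (3 of 15 for 1 h). The mean condition effect is not diluted by bedtime spread.

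No sample size, power or significance level in the documents is affected.

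**What to change.** 1. **Schedule.** Reconcile the 3-hour post-wake period with the 10:00 discharge, and check the 09:00 end of sampling for bedtimes after 01:00. Which passage changes is for the sponsor to decide.
2. **VAS.** Replace the complete-cell ANOVA with a mixed model that has a participant effect and accepts incomplete cells, fitted to evening and morning separately. Alternatively, restrict the analysis to the window common to all participants. The mixed model adds assumptions. The common window loses edge cells: with bedtimes of 22:00–00:00 and discharge at 10:00, each participant keeps 6 of 8 ratings.
3. **Melatonin.** State the time axis in Statistical Procedures, consistent with Fig. 3. Report scheduled lights-out by condition. Present both a clock-hour and a lights-out-aligned analysis, and let the sponsor name the primary one in advance. A common window on the lights-out axis drops 1 of 15 point samples for bedtimes of 22:00–23:00 and 2 of 15 for 22:00–00:00.

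The cost is a few sentences of text and some extra analysis. No samples or visits are added.

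### The within-subjects ANOVA planned for hourly melatonin and VAS needs every condition-by-time cell filled, and no rule in the plan keeps participants who have gaps

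*Combined protocol and SAP*

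**What the plan says.** The Statistical Procedures section of the combined protocol and SAP gives one method for the melatonin, VAS and neuropsychological values from the laboratory visits: "Two-way within subjects ANOVA for repeated measures (factors: condition x time) will be used". Single-value sleep measures and sleep questionnaires go to paired t-tests. The only fallback is a switch to non-parametric equivalents when data look non-normal. The section does not define the time factor. Neither it nor the Study Design section has a rule for missed samples, incomplete visits, imputation, interpolation, replacement of participants or the analysis population.

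The Study Design section sets the data structure:

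- Melatonin: "Blood (3 ml/sample) will be collected continuously (1x/h) from 19:00-09:00". These are fixed clock times that run through the sleep episode.
- VAS: "Each hour spent awake in the laboratory, participants will complete a 15-item visual analogue scale". No number of assessments or clock times is given.
- Sleep timing: "The sleep episode will be scheduled based on their habitual sleep patterns during the previous week at home".
- Second period: after a 4-week washout and a further week of lenses, "they will return to the lab for the second overnight visit".

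**The concern.** A classical two-way within-subjects ANOVA works on a full grid: each participant must have a value in every combination of condition and time. When one is missing, the usual behaviour is to exclude the whole participant. With a long hourly series at two visits, a low rate of missed draws can therefore remove a much larger share of people. The stated fallback does not help, because the usual non-parametric counterparts (Friedman, Wilcoxon signed-rank) also need complete blocks or pairs.

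For the VAS, gaps may arise without anything going wrong. If time is clock hour, people with different bedtimes fill different cells. Restricting the analysis to hours when everyone was awake could then remove pre-bed hours, which are when the lenses are worn.

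At stake are precision and a clear account of who is in the analysis. The cause is the choice of method as well as the missing rule, because a standard alternative uses the same data without the loss.

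**Working it through.** The plan states no sample size, power, dropout rate or missed-sample rate, so there is no figure of its own to reproduce. All rates below are assumptions.

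**1. Cells per participant (melatonin).** Hourly from 19:00 to 09:00 with both ends included is 15 draws. Over two visits, 15 × 2 = 30 cells. If the wording means 14 hourly intervals, the count is 28.

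**2. Draws missed independently at rate q.** Share of participants complete = (1 − q)^30.

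| q | 30 cells | 28 cells |
|---|---|---|
| 1% | 0.99^30 = 74% | 75% |
| 2% | 0.98^30 = 55% | 57% |
| 3% | 0.97^30 = 40% | 43% |
| 5% | 0.95^30 = 21% | 24% |

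An analysis of all available samples would lose about q of the cells (2% at q = 2%) and no whole participant for this reason.

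**3. Losses clustered by visit.** One catheter serves each visit, so failures may come together. With a share v of visits giving an unusable series, share complete = (1 − v)^2: 0.95² = 90%, 0.90² = 81% and 0.85² = 72%. Here the mixed model gains little, because an affected participant has little or nothing from one condition.

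**4. Illustration of precision.** Assume 20 participants, 10% dropout before visit 2, and an effect giving 80% power with 20 in a two-sided paired t-test at 0.05.

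- Dropout alone leaves 20 × 0.9 = 18, with power about 75%.
- Complete-case analysis leaves 20 × 0.9 × 0.74 ≈ 13 at 1% independent misses (power about 59%).
- It leaves 20 × 0.9 × 0.545 ≈ 10 at 2% (about 46%) and 20 × 0.9 × 0.215 ≈ 4 at 5% (about 16%).

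These powers are for one paired contrast, not for the condition-by-time interaction.

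**5. VAS by clock hour.** Take bedtimes of 22:00 and 24:00 with the planned 8-hour sleep episode. The first person is asleep 22:00–06:00 and the second 00:00–08:00. Hours 22:00–24:00 are filled only for the second, and 06:00–08:00 only for the first. Keeping common hours removes the second person's whole 2-hour lens period.

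A simulation assumed 20 people, bedtimes centred on 23:00 with a between-person SD of 0.5 to 1.5 h and a visit-to-visit SD of 0.25 to 0.5 h, over clock hours 19:00 to 09:00. Essentially nobody filled every clock-hour cell seen in the group. Only about 1.4 to 4.6 of about 9 to 13 hours were common to all, and about 28% to 52% of people had different waking-hour patterns at their own two visits.

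**6. Outcomes not affected in the same way.** Melatonin is drawn at fixed clock hours, asleep or awake, so differing sleep times empty no melatonin cell. The neuropsychological battery has about 4 cells per person and is much less exposed to gaps.

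**The case against.** The strongest reply is that exclusion of incomplete participants is how the method usually behaves, not something the plan states, and that analysts could fill an isolated gap. That is true, but the plan provides for no such step, so the default stands until something replaces it.

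It can also be said that independent misses are the steepest assumption. This stands: with failures clustered by visit the loss is far smaller, so both patterns have to be shown.

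On the VAS, the time factor is undefined and the figure showing the laboratory visit is not available here. The lens period is anchored to bedtime; if time were indexed the same way, the pre-bed hours would line up. The VAS concern is therefore conditional on clock-hour indexing. Even with alignment, a common admission time (about 18:00) and discharge time (10:00) leave people with unequal numbers of waking hours before and after sleep, so a full-grid ANOVA would still need truncation.

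Three stronger readings are tempting and should not be drawn:

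- **That phase 1 dropouts are lost because of the ANOVA.** The paired t-tests lose them too, and one period tells little about condition under any model.
- **That the loss is selective because poor sleepers disturb the catheter more.** Nothing in the documents supports this. Comparisons are within person, so it would bias the contrast only if the effect differed in those people or missingness depended on condition.
- **That differing wake hours damage the melatonin analysis.** The fixed draw times rule this out.

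**Conclusion.** The concern holds in a limited form. The plan pairs a method that needs a complete grid with hourly series that may have gaps, and says nothing about incomplete participants. For melatonin, the share kept runs from 74% down to 21% for 1% to 5% independent misses, and from 90% down to 72% for 5% to 15% unusable visits. These figures rest on assumed rates, on about 30 cells per person, and on the usual exclusion of incomplete participants.

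A reader might infer that the trial is already small and will lose much of its sample. The documents call it a pilot but give no sample size, missed-draw rate or dropout rate, so neither statement can be verified. The VAS problem is real only if time is clock hour; what is certain is that the time axis is undefined. The change is worth making because it is cheap and the alternative uses the data better, not because a particular loss has been shown.

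**What to change.** Replace the ANOVA for the hourly outcomes with a linear mixed model fitted to all available samples:

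- fixed effects for condition, time, condition-by-time and period;
- random effects for participant and participant-by-visit;
- a serial within-visit covariance such as AR(1), because the random effects alone would imply equal correlation between all hours of a visit;
- Kenward-Roger degrees of freedom.

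Index VAS time by hours before lights-out and hours after waking. For single-value outcomes, use condition and period with a random participant effect only; with one value per visit, a participant-by-visit effect cannot be separated from residual error. State that participants with partial data are kept, and how missed samples and one-phase participants are handled. A simpler option for melatonin is a per-visit summary, such as area under the curve, with a stated minimum number of samples.

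The cost is analysis-plan wording and a standard routine, with no new data. The model relies on a missing-at-random assumption and a chosen covariance structure, and it recovers little from participants who complete only one phase.
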